6.2. Time Point Algorithms

6.2.1. Study Day

The date of informed consent/assent (Visit 1), will be considered study day 0. Days prior to study day 0 will be negative. Study days will be calculated as follows only when the full assessment date is known (ie, partial dates will have missing relative days).

Study day will be calculated as follows:

Date of Assessment – Date of Informed Consent.

The relative day on study drug will be calculated as follows:

Date of assessment – date of the first study drug administration +1.

6.2.2. Windows

For analysis purposes, the visit numbers will be allotted into windowed visits, as illustrated in [Table 2](#).

Table 2: Analysis Windows

Week	Visit	Scheduled Study Day	Visit Window for Analysis (Days)
Screening/Baseline	Visit 1	0	Day -13 to Day 0
Month 1	Visit 2	30	Day 1 – Day 60
Month 3	Visit 3	90	Day 61 – Day 135
Month 6	Visit 4	180	Day 136 – Day 225
Month 9	Visit 5	270	Day 226 – Day 315
Month 12	Visit 6	360	Day 316 – Day 405
Month 15	Visit 7	450	Day 406 – Day 495
Month 18	Visit 8	540	Day 496 – Day 585
Month 21	Visit 9	630	Day 586 – Day 675
Month 24	Visit 10	720	Day 676 – Day 765
Month 27	Visit 11	810	Day 766 – Day 855
Month 30	Visit 12	900	Day 856 – Day 945
Month 33	Visit 13	990	Day 946 – Day 1035
Month 36	Visit 14	1080	Day 1036 – Day 1125
Month 39	Visit 15	1170	Day 1126 – Day 1215
Month 42	Visit 16	1260	Day 1216 – Day 1305
Month 45	Visit 17	1350	Day 1306 – Day 1395
Month 48/Final Visit	Visit 18	1440	Day 1396 – Completion

If two visits fall within the window, then the closest one will be selected. If two visits are equal distance from the nominal visit day, then the first one is used.

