8.4. Withdrawal Criteria/Study Discontinuation

Patients may withdraw from the study at any time without stating a reason and without prejudice to further treatment. The Investigator may withdraw a subject from the study and discontinue study treatment and assessments at any time due to safety concerns. Full skin examination will be performed at each visit. If ZORBLISA causes any significant rash that has not occurred previously in the subject, the Investigator should consider discontinuing the subject. In addition, if lesions appear to significantly worsen above the normal cycle seen in the patient, with use of ZORBLISA, the investigator should consider discontinuing the subject.

Early discontinuation of any subject who has given informed consent /assent to participate will be recorded including the reason for discontinuation. The primary reason for a subject withdrawing prematurely will be selected from the following standard categories of early discontinuations.

- 1. Adverse Event and Adverse Reactions: Clinical events occurred that are reported that in the medical judgment of the investigator are grounds for discontinuation in the best interests of the subject.
- 2. Withdrawal of Consent: The subject desired to withdraw from further participation in the study. The subject is not obligated to provide any reason for withdrawal of consent, but where a reason is given this will be recorded on the eCRF.
- 3. Protocol Violation: The subject failed to adhere to the protocol requirements, at the investigator's discretion.
- 4. Lost to Follow-Up: The subject stopped coming for visits and study personnel were unable to contact the subject.
- 5. Other: The subject was terminated for a reason other than those listed above, such as, termination of study by Sponsor.

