11. STUDY SCHEDULE

Procedure Visit	1 Screening/Baseline	2 Month 1	3 Month 3	4 Month 6	5 Month 9	6 Month 12	7 to 17 Month 15 to 45 ^a (Every 3 months)	18 Month 48 Final Visit/ Early Termination
Study Day (± 7 Days for Visits 2 – 18)	0	30	90	180	270	360	450 to 1350	1440
Informed consent /assent signed	Х							
Inclusion/Exclusion assessment	Х							
Demographic, medical and medication history ^b	Х							
Physical examination ^c	Х							Х
Height, weight, and temperature ^c	Х							Х
Assess BSA of lesional skin ^d	Х	Х	Х	Х	Х	Х	Х	Х
Assess BSA of wound burden ^d	Х	Х	Х	Х	Х	Х	Х	Х
Assess target wound via ARANZ ^e	Х	Х	Х	Х	Х	Х	Х	Х
Bandage history	Х		Х	Х	Х	Х	Х	Х
Urine pregnancy test (females of child-bearing potential only) $^{\rm f}$	X		Х	Х	Х	Х	Х	Х
Dispense ZORBLISA ^g	Х		Х	Х	Х	Х	Х	
Collect ZORBLISA for the purpose of drug accountability			Х	Х	Х	Х	Х	Х
Collect all ZORBLISA								Х
Monitor adverse events ^h	Х	Х	Х	Х	Х	Х	Х	Х
Monitor use of concomitant medications	Х	Х	Х	Х	Х	Х	Х	Х

CONFIDENTIAL

- a. Patients will return once every 3 months for Visit 7 (Month 15; day 450), Visit 8 (Month 18; day 540), Visit 9 (Month 21; day 630), Visit 10 (Month 24; day 720), Visit 11 (Month 27; day 810), Visit 12 (Month 30; day 900), Visit 13 (Month 33; day 990), Visit 14 (Month 36; day 1080), Visit 15 (Month 39; day 1170), Visit 16 (Month 42; day 1260), and Visit 17 (Month 45; day 1350).
- b. Demographic, medical and medication history collected during SD-005 will be utilized as the baseline information for SD-006
- c. The physical examination, as well as, height, weight, and temperature performed at the final visit for SD-005 will be utilized as the baseline assessment for SD-006 unless Visit 1 is ≥ 14 days after the final SD-005 visit, in which case the assessment will be repeated. A complete physical examination, as well as, height, weight, and temperature will be performed at visit 18.
- d. The BSA assessments of lesional skin and wound burden performed at the final visit for SD-005 will be utilized as the baseline assessment for SD-006 unless Visit 1 is \geq 14 days after the final SD-005 visit in which case the assessment will be repeated. The BSA assessments of lesional skin and wound burden will be performed at visits 2 through 18.

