5. CHANGES IN THE CONDUCT OF THE STUDY OR PLANNED ANALYSIS

5.1. Changes in the Conduct of the Study

There were two amendments in the protocol. The first amendment was finalized on 2 December 2015, the second amendment was finalized on 10 November 2016. The second amendment extends study period from 360 days to 1440 (48 months) days. On June 4, 2018, a Dear Doctor Letter was sent to all sites to discontinue the applications of SD-101 cream immediately, bring the patients back to the sites for the end of study visit and collect all the remaining tubes of SD-101, because the manufacturer of SD-101 had received a warning letter from the FDA for several violations of GMP regulations that, although not mentioning SD-101, may have resulted in the adulteration of SD-101.

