7.3. Handling of Dropouts or Missing Data

Dropout patients will not be replaced in this study. Missing data will not be imputed unless specified otherwise in the following section.

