8.6. Analysis of Efficacy Parameters

8.6.1. Analysis of BSAI

No comparison between treatment groups will be performed. The comparison to baseline will be done by visit in Placebo → SD-101-6.0 group using the paired t-test.

- Change in extent of lesional skin based on BSAI at each visit compared to baseline.

To evaluate post-baseline BSAI of lesional skin, both change from baseline and percentage change from baseline will be explored using descriptive statistics. Change from baseline will be calculated as the post-baseline measurement minus the baseline value. Percentage change from baseline will be calculated as the change from baseline divided by the baseline value times 100.

Graphs of the mean change and mean percentage change from baseline over time will also be presented.

- Change in total wound burden based on BSAI at each visit compared to baseline.

This assessment will be analyzed using the same approach for lesional skin as the total body wound burden to both change from baseline and the percentage change from baseline.

Graphs of the mean change and mean percentage change from baseline over time will also be presented.

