8.7.8.2. Physical Findings

Physical examination findings will be summarized in shift tables that will be presented to display the shift in the normal range categories (normal vs. abnormal) from baseline to the final evaluation. Baseline is defined in section [6.3](#).

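### SAP 6.2.2 can leave an early-termination BSAI value out of every planned BSAI statistic, and counts the values it keeps as ordinary scheduled visits

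*SAP*

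**What the plan says.** - **Collection.** Protocol 11 makes Visit 18 both the Month 48 visit and the early-termination visit, and footnote d says: "The BSA assessments of lesional skin and wound burden will be performed at visits 2 through 18". A patient who stops early therefore has both BSAI assessments at the termination visit.
- **Windows.** SAP 6.2.2 (Table 2) allots visits by study day. The last row is bounded as "Day 1396 – Completion". When two visits share a window, "If two visits fall within the window, then the closest one will be selected"; ties go to the first visit. Early termination is not mentioned.
- **Analysis.** SAP 8.6.1 plans "Change in extent of lesional skin based on BSAI at each visit compared to baseline", and treats wound burden in the same way. Descriptive statistics, graphs and the paired t-test in the former-placebo group are all by visit. SAP 7.3 adds: "Missing data will not be imputed unless specified otherwise in the following section". The SAP names no last-value or worst-value summary and no listing for BSAI.
- **Reasons for stopping.** Protocol 8.4 asks the investigator to consider discontinuation "if lesions appear to significantly worsen above the normal cycle seen in the patient, with use of ZORBLISA". SAP 5.1 reports that on 4 June 2018 sites were told to "discontinue the applications of SD-101 cream immediately, bring the patients back to the sites for the end of study visit".

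**The concern.** Protocol 8.4 makes marked lesion worsening a reason to consider stopping, so some termination assessments may record a patient's worst skin. Under the window rule, the study day decides whether that value is reported. With a scheduled visit on Day 180 and withdrawal on Day 200, both fall in the Month 6 window (Day 136 to 225). Day 180 is kept and Day 200 is lost. The Day 200 value then enters no mean, maximum, graph or test.

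The termination values that survive are treated as scheduled visits. This includes the June 2018 end-of-study visits, which followed an instruction to stop the cream. The SAP sets no on-treatment limit for BSAI, although it was written with the stop known.

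BSAI is the only whole-body measure of disease extent scheduled at every visit, and SAP Table 1 (footnote e) says target wound data were not captured at the end-of-study visit.

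**Working it through.** The documents give no discard rate, so there is no planned figure to reproduce. The share can be counted exactly from Table 2.

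**Inputs from the documents.** Month 1 window: Day 1–60, nominal 30. Month 3: Day 61–135, nominal 90. Months 6 to 45: fourteen 90-day windows, each with 44 days before nominal and 45 after. Scheduled visits: nominal ± 7 days.

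**Assumptions not in the documents.** The termination visit is separate from a scheduled visit and equally likely on any day. The scheduled visit is at nominal + d, with d uniform on the whole days −7 to +7.

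**Rule.** Let a window have A days before nominal and B after. The termination value is lost if it comes after the scheduled visit and is no closer to nominal.
- d ≥ 0: B − d losing days.
- d < 0: B + 1 − |d| losing days.
- Sum over the 15 values of d: 15B − 49, out of 15(A + B) possibilities.

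| Window | A, B | Lost / possible | Share |
|---|---|---|---|
| Month 1 | 29, 30 | 401 / 885 | 45.3% |
| Month 3 | 29, 45 | 626 / 1110 | 56.4% |
| Each 90-day window | 44, 45 | 626 / 1335 | 46.9% |

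**Termination anywhere in Day 1–1395.** (401 + 626 + 14 × 626) / (885 + 1110 + 14 × 1335) = 9791 / 20685 = **47.3%**.

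**Termination in Day 1–360 only.** The part of the Month 12 window up to its nominal day adds 667 possibilities and no losses: (401 + 3 × 626) / (885 + 1110 + 2 × 1335 + 667) = 2279 / 5332 = **42.7%**.

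**20% of scheduled visits missed.** A missed visit leaves the termination value alone in its window, so the shares are multiplied by 0.8: 47.3% becomes 37.9% and 42.7% becomes **34.2%**. The range is therefore about 34–47%.

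**Sensitivity.**
- Exponential dropout times (median 180 to 1440 days), all visits attended: 44.0–46.5%.
- All scheduled visits exactly on nominal: 51.1%.
- A share c of termination visits is itself the scheduled visit: 47.3% × (1 − c), giving 37.9% at c = 0.2, 23.7% at c = 0.5 and 9.5% at c = 0.8.

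**Effect on one visit mean (extreme assumed case).** Assume 75 patients in a group (half of the planned 150). Ten are withdrawn at a change of +15 and the others are at −3, so each lost value differs by 18 points. About 45% are lost, spread over the 11 rows from Month 1 to Month 30. Then 10 × 0.45 / 11 = 0.41 values lost per row, and 0.41 × 18 / 75 = **0.10 point**.

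**The final row.** 4 June 2018 minus 1396 days is 8 August 2014. Only patients who consented by then could reach the row before the stop. Enrolment dates are not given, so the row labelled Final Visit may hold few patients or none.

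**The case against.** **Decision at a scheduled visit.** Protocol 8.4 sets a full skin examination at each visit beside its advice on stopping. If withdrawal is decided there, the scheduled value is the termination value and is usually kept. This stands. The 34–47% applies only to separate termination visits, and a reader should not apply it to every patient withdrawn for worsening.

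**Existing coverage.** Reasons for discontinuation are summarised (SAP 8.1, 8.7.6). Adverse events leading to withdrawal are tabulated, and those patients get narratives (SAP 8.7.5). This stands too: worsening that qualifies as an adverse event stays visible. However, the SAP does not require its BSAI extent to be shown.

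**The physical-examination contrast.** SAP 8.7.8.2 plans to "display the shift in the normal range categories (normal vs. abnormal) from baseline to the final evaluation". It would be wrong to infer a last-value rule withheld from BSAI, because the physical examination is scheduled only at baseline and Visit 18.

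**Another reading of Table 2.** If termination visits kept their Visit 18 label, none would be lost. The Day 1396 bound and the remark in SAP 6.4.1 that late data will be limited speak against this. It would also mix values from any study day into a Month 48 row.

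**Stronger inferences.** A reader might conclude that dropping these values distorts the visit means or the paired t-test. The arithmetic does not support that. A gap between a last-assessment mean and the rows after patients have left comes mainly from dropout and would remain if every termination value were kept. A reader might also conclude that the late rows are heavily contaminated by off-treatment values. The documents give neither the interval between stopping and the end-of-study visit nor the study days at the stop, so no share can be established.

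**Conclusion.** The concern holds as a reporting gap. The stated rule, read literally, excludes some termination BSAI values from all planned BSAI statistics; the Day 180 and Day 200 example needs no numerical assumption. The size, about 34–47%, does rest on assumptions: separate termination visits, timing unrelated to the schedule, scheduled visits within ±7 days and 0–20% missed. The loss is smaller the more often withdrawal is decided at a scheduled visit.

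Retained values are pooled with scheduled ones whether or not the cream had been stopped; the extent of that mixing cannot be determined. BSAI is a secondary, open-label, uncontrolled endpoint and the effect on a visit mean is small. The change is therefore a cheap improvement to what is shown for withdrawn patients. It is not a correction on which the study's conclusions depend.

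**What to change.** Amend SAP 6.2.2 and 8.6.1:

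1. Add a last post-baseline assessment row to the lesional-skin and wound-burden tables, by SD-005 group and overall. Use each patient's last BSAI whether or not a window selected it.
2. Flag values in that row taken more than 7 days (the protocol visit tolerance) after the last application. For patients stopped by the letter, count from 4 June 2018.
3. Rename the Month 48/Final Visit row to Month 48.
4. Score the new row exactly as the visit rows are scored, so that the two can be compared.

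The cost is SAP wording, one row in each of two tables and a flag, from data already collected. No daily use data exist (SAP 6.5.1, 8.7.1), so the last application date must come from the administration dates that Protocol 17.5 requires in the patient file. The new row mixes study days, has no control and is pessimistic for patients who withdraw at their worst. It should stand beside the by-visit rows and not replace them.

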6.3. Baseline Definition and Assessments

6.3.1. Baseline definition

For most cases, the baseline visit (Visit 1) will occur at Visit 5 for SD-005. Exceptions are detailed below.

The Body Surface Area Index (BSAI) assessments of lesional skin and wound burden performed at the Visit 5 for SD-005 will be utilized as the baseline assessment for SD-006 unless Visit 1 is ≥ 14 days after the final SD-005 visit in which case the assessment will be repeated.

The urine pregnancy test performed at the final visit for SD-005 will be utilized for entry (Visit 1) into SD-006 only if the visits occur on the same day, otherwise, urine pregnancy test will be performed at Visit 1 as baseline assessment for SD-006.

The physical examination performed at the final visit for SD-005 will be utilized as the baseline assessment for SD-006 unless Visit 1 is ≥ 14 days after the final SD-005 visit, in which case a physical examination will be repeated and used as baseline assessment for SD-006.

The ARANZ picture that documents target wound status at the final visit for SD-005 will be utilized to determine target wound area unless Visit 1 is ≥ 14 days after the final SD-005 visit, in which case the assessment will be repeated on the same wound. For target wounds that are not closed by the end of Study SD-005, the ARANZ picture and calculation of target wound area at the final visit for Study SD-005 will be used as the baseline area size of the target wound for SD-006. The wounds that are closed at the end of study SD-005 will not be followed up and analyzed.

6.3.2. Baseline assessments

The following screening and baseline assessments will be conducted prior to initial application of study treatment:

- Informed consent/assent signed and dated.
- Inclusion/exclusion assessment.
Medical and medication history (including disease subtype) obtained from SD-005. Adverse events continuing in study SD-005 and those originating within the gap between studies SD-005 and SD-006 will be transcribed into Medical History.
Note: All Adverse Events (AEs) experienced in SD-005 and medical events occurring between the end of SD-005 and the enrollment into SD-006 after completion of SD-005 should be noted in the medical history for SD-006 at Visit 1 only.
- Demographics (date of birth, race, gender, ethnicity) obtained from SD-005.
- Vital Signs (height/length, weight, temperature) obtained from final visit of SD-005 unless Visit 1 is ≥ 14 days after the final SD-005 visit in which case the assessment will be repeated.
- Physical examination obtained from final visit of SD-005 unless Visit 1 is ≥ 14 days after the final SD-005 visit in which case the assessment will be repeated.
- BSAI of wound burden obtained from final visit of SD-005 unless Visit 1 is ≥ 14 days after the final SD-005 visit in which case the assessment will be repeated.
- BSAI of lesional skin obtained from final visit of SD-005 unless Visit 1 is ≥ 14 days after the final SD-005 visit in which case the assessment will be repeated.
- Assess target wound via ARANZ; if the target wound has not healed by the final visit of the SD-005 study, the same target wound will be assessed in SD-006 using ARANZ until the wound has healed. The ARANZ picture for target wound will be utilized as the baseline for SD-006 unless Visit 1 is ≥ 14 days after the final SD-005 visit in which case the assessment will be repeated.
- If target wound has healed, assess for scarring.
- Bandage history.

- The urine pregnancy test performed at the final visit for SD-005 will be utilized for entry (Visit 1) into SD-006 only if the visits occur on the same day, otherwise, urine pregnancy test will be performed at Visit 1 as baseline assessment for SD-006.
- Dispense sufficient SD-101-6.0 until next study visit.

6.4. Efficacy Assessments

6.4.1. Change in Body Surface Area Index (BSAI)

- Change in lesional skin based on BSA estimates at Month 1, 3, 6, 9, 12, 15, 18, 21, 24, 27, 30, 33, 36, 39, 42, 45, and 48 compared to baseline will be measured using the Body Surface Area Index (BSAI), where change is defined as the corresponding month value minus the baseline value.
- The BSAI is a global measure of disease extent with weighting factors. The BSA affected with lesional skin will be calculated at baseline and at each visit to assess the total affected area before and after using the product. The BSAI of lesional skin will be assessed as listed in Section 11.1.
- Change in total body wound coverage based on BSAI estimates at Months 1, 3, 6, 9, 12, 15, 18, 21, 24, 27, 30, 33, 36, 39, 42, 45, and 48 compared to baseline will be measured using the BSAI, where change is defined as the corresponding month value minus the baseline value. The BSAI of wounds will be assessed as listed in Section 11.2. Due to the termination of the study data at later time points will be limited.

6.5. Safety Assessments

6.5.1. Extent of Exposure and Compliance to Study Treatment

SD-101-6.0 will be applied once a day to the entire body for a period of 1440 days. No daily use data are collected in this study.

6.5.2. Adverse Events

Treatment-emergent adverse events (TEAEs) are any untoward medical occurrence in a patient, administered a medicinal product and which does not necessarily have to have a causal relationship with this treatment. An adverse event (AE) can therefore be any unfavorable and unintended sign (including an abnormal laboratory finding, for example), symptom, or disease temporally associated with the use of a medicinal product, whether or not considered related to the medicinal product. AEs may include the onset of new illness and the exacerbation of pre-existing conditions. Treatment-emergent AEs will be collected after signing the informed consent/assent through the last study visit. If there is a gap between the completion of the Study SD-005 and the start of Study SD-006, adverse events starting after the last study day or changing in severity or relationship to treatment within the gap will be recorded in the medical history for study SD-006. Continuing adverse events will be also captured in medical history for the extension study SD-006.

Medical review will take place to determine if any of AEs could be potentially related to the contamination of the study medication during the manufacturing process. The investigator's

verbatim term of both serious and non-serious AEs will be mapped to system organ class (SOC) and preferred terms (PTs) using the 19.1 version of the Medical Dictionary for Regulatory Activities (MedDRA). Partial dates will be imputed as the following:

1. If year is not missing and is after the year of first application of study drug:
 - a. If Month is missing, then Month will be imputed as January.
 - b. If Day is missing, then Day will be imputed as the first of the month.
2. If year is not missing and is the same as the year of the first application of study drug:
 - a. If Month is missing, then impute the Month as the month of the first application of study drug.
 - b. If Day is missing but Month is on or after the month of first application of study drug, then impute Day as the first day of - the month.
 - c. If the Day and Month are missing then impute Day and Month as the Day and Month of the first study drug application.
3. If year is missing then impute the year as the year of the first study drug application:
 - a. If Month is missing, then impute the Month as the Month of the first study drug application.
 - b. If Day is missing, then impute the Day as the day of the first study drug application.
4. If the start date is completely missing, but the AE is either ongoing or the stop date is after the first date of drug application, then impute the start date as the first date of study drug application.
5. If using the above rules, the stop date is before the start date, then leave the stop date missing and assume that AE is treatment-emergent for the purpose of the analysis.

Completely missing stop dates will not be imputed. The partial stop dates will be imputed as follows:

1. If the year is missing, the stop date will not be imputed.
2. If the month is missing, then the month will be imputed as December.
3. If the day is missing, then the day will be imputed as the last day of the month.

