8.2. Inclusion Criteria

Patients must meet all of the following inclusion criteria to be eligible for enrollment into the study.

- 1. Informed Consent form signed by the subject or subject's legal representative; if the subject is under the age of 18 but capable of providing assent, signed assent from the subject.
- 2. Subject (or caretaker) must be willing to comply with all protocol requirements.
- 3. Patients who completed the SD-005 study (on study drug at Visit 5).

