13.3. Adverse Events

Adverse events may be volunteered spontaneously by the patient or discovered as a result of general, non-leading questioning. All adverse events should be recorded in the Case Report Form. Adverse events will be collected after signing the informed consent/assent through Visit 18. Information on AEs will be followed to 30 days after the last dose of study drug has been administered.

In the case of withdrawal due to an AE/SAE, the patient will be followed until resolution of the AE, or until in the opinion of the Investigator the event has stabilized, or the investigator does not expect any further improvement or worsening of the subject's condition, and the patient is referred to their primary physician for appropriate management of the ongoing event. Reasonable efforts will be made to contact a patient who fails to attend any follow-up appointments, in order to ensure that he/she is in satisfactory health.

Note: All AEs experienced in SD-005 and medical events occurring between the end of SD-005 and the enrollment into SD-006 after completion of SD-005 should be noted in the medical history for SD-006 at Visit 1 only.

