8.7.2. Adverse Events by Preferred Term and System Organ Class

For the first interim analysis serious AEs will be mapped to system organ class (SOC) and preferred terms (PTs) using the 19.1 version of MedDRA.

If there is a gap between the completion of the study SD-005 and the start of the study SD-006, adverse events starting after the last study day or changing the severity or relationship to treatment within the gap will be counted as medical history for the extension study SD-006. Continuing adverse events will also be captured in medical history for the extension study SD-006. If the severity or relationship to treatment changed on or after the first dose of study medication, then that AE is considered a TEAE after that change.

If an AE started after signing an informed consent/assent but before the first dose of study medication was taken in the study SD-006, then such an AE is non treatment-emergent.

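### For patients continuing from SD-101-6.0, adverse events between the last SD-005 study day and the first SD-006 application stay out of the SD-006 TEAE and TESAE tables unless they later change or lack a start date, and SAP 6.5.2 and 8.7.2 disagree on when treatment-emergence begins

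*SAP*

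**What the plan says.** **Gap events.** If there is a gap between the two studies, SAP 6.5.2 states that "adverse events starting after the last study day or changing in severity or relationship to treatment within the gap will be recorded" in the SD-006 medical history. SAP 8.7.2 carries this into the analysis: such events "within the gap will be counted as medical history for the extension study SD-006". Protocol 13.3 is the source of the rule. It sends "medical events occurring between the end of SD-005 and the enrollment into SD-006" to the Visit 1 medical history, together with all SD-005 AEs.

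**Events between consent and first dose.** Under SAP 8.7.2, if an event begins after consent but "before the first dose of study medication was taken in the study SD-006, then such an AE is non treatment-emergent".

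**Start of the treatment-emergent period.** SAP 6.5.2 says something different: "Treatment-emergent AEs will be collected after signing the informed consent/assent through the last study visit".

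**Who is affected.** Protocol 8.2 admits patients who completed SD-005 while on study drug at Visit 5. The SAP abbreviation list and SAP 7.1 define two reporting groups by SD-005 arm, Placebo → SD-101-6.0 and SD-101-6.0 → SD-101-6.0. None of the rules above distinguishes between them.

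**Outputs.** SAP 8.7.3 and 8.7.5 tabulate TEAEs and TESAEs. Non treatment-emergent AEs and SAEs are listed, and a listing of all SAEs with patient narratives is planned. SAP 8.4 summarizes and lists medical history.

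**The concern.** For a former placebo patient, anything before the first SD-006 dose is pre-treatment and the rule is right. For a patient coming from SD-101-6.0, the same days follow directly on active treatment with the same product. A reaction that surfaces then is plausibly drug-related, yet it is filed as history.

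Worsening is handled the same way. SAP 8.7.2 counts only a change in severity or relationship on or after the first SD-006 dose. A moderate event that becomes severe in the gap and stays severe is never a TEAE.

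Long-term safety is the primary objective, and this group has the longest exposure to SD-101-6.0. Within the SD-006 tables the omission can only lower its counts. SAP 6.5.2 also plans a medical review of AEs for a possible link to product contamination. As worded, events held only as medical history may fall outside that review.

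The conflict between 6.5.2 and 8.7.2 matters whether or not gaps are common: a programmer cannot follow both.

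**Working it through.** The plan gives no figure to reproduce. The check traces each type of event in a continuing SD-101-6.0 patient through the rules to its output.

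| Event | Rule | SD-006 output |
|---|---|---|
| Starts or worsens in the gap, before consent, no later change | SAP 6.5.2, 8.7.2; protocol 13.3 | Medical history only (SAP 8.4) |
| Starts after consent, before first dose, no later change | SAP 8.7.2 | Listing of non-TEAEs; if serious, also SAE listing and narrative |
| Either of these, with severity or relationship changing on or after first dose | SAP 8.7.2 | TEAE table from the change onward; TESAE table if serious |
| Start date fully missing, and ongoing or stopping after first application | SAP 6.5.2 and 8.7.4.1 | Dated to first application, so TEAE |

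The last row has an odd result: an event recorded as an AE without a start date can be counted, while the same event with a known date in the gap is not.

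**The contradiction.** Take an event that starts after consent and before the first SD-006 application. The collection sentence in 6.5.2 calls it treatment-emergent, and 8.7.2 calls it non treatment-emergent. Protocol 13.3 says only that adverse events are collected from consent, without that qualifier, so 8.7.2 is the version consistent with it.

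**Scale.** SAP 6.3.1 says that in most cases SD-006 Visit 1 takes place at SD-005 Visit 5, so most patients have no gap. The documents do not give the number with a gap, its length or the AE rate. They set no maximum gap, and they provide for repeat baseline assessments when it reaches 14 days. Two illustrations follow, both resting on assumptions.

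1. Share of a patient's observed time that falls in the gap, at a constant event rate = gap days / (gap days + SD-006 days). The SD-006 durations are the 1440 days now planned and the 360 days before the second amendment (SAP 5.1).
   - 13-day gap: 13/1453 = 0.9%; 13/373 = 3.5%.
   - 30-day gap: 30/1470 = 2.0%; 30/390 = 7.7%.

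   These shares apply only to patients who have a gap.

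2. Expected gap events = patients × share with a gap × gap days/365.25 × AEs per patient-year. Assume 75 continuing patients, half of the approximately 150 expected; the split is not given.
   - 5%, 7 days, 2 per year: 75 × 0.05 × 7/365.25 × 2 = 0.14
   - 10%, 14 days, 4 per year: 75 × 0.10 × 14/365.25 × 4 = 1.15
   - 20%, 21 days, 4 per year: 75 × 0.20 × 21/365.25 × 4 = 3.45
   - 25%, 30 days, 6 per year: 75 × 0.25 × 30/365.25 × 6 = 9.24

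The spread from 0.14 to 9.24 shows how far the answer depends on unknown inputs. It is not an estimate.

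**The case against.** The strongest reply is that the harm depends on documents not available here. If SD-005 follows patients after its last dose, events soon after that dose belong to SD-005, and the medical-history rule avoids counting them twice. This stands: the point can be made only about the SD-006 tables.

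Four stronger readings are tempting, and the documents do not support them.

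- *The events vanish from safety reporting.* They do not. The exceptions in the table bring some back as TEAEs, post-consent events are listed, and SAEs after consent have a listing and narratives.
- *The plan's own risk period covers the gap.* Protocol 13.3 says "Information on AEs will be followed to 30 days after the last dose of study drug has been administered". That concerns follow-up of AE information in SD-006. It sets no treatment-emergent window and says nothing about the last SD-005 dose.
- *The two groups' TEAE columns are on different bases.* They share one anchor, the first SD-006 dose, and SAP 7.1 plans no comparison between groups. A different rule inside the tables for one group would create the very inconsistency complained of.
- *Events on the drug are excluded.* At most this could apply between consent and the first SD-006 dose in patients with no gap. Consent and dispensing both take place at Visit 1, so that interval should be short. The gap itself comes after SD-005 is completed.

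There is also a practical objection. Rows inside the TESAE tables would need seriousness, and often causality, for events recorded as medical history. The documents do not say that those fields exist. The SAP describes the June 2018 letter stopping treatment as a past event, so data not collected may not be recoverable. This also stands, and it is why the remedy below is a separate display.

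**Conclusion.** The point holds in a limited form. For the SD-101-6.0 → SD-101-6.0 group, events that start or worsen between the last SD-005 study day and the first SD-006 application are left out of the SD-006 TEAE and TESAE tables unless they change on or after the first dose or have a fully missing start date. This is a one-directional omission on the primary objective. It is probably small, because most patients have no gap, and its size cannot be estimated from the documents. Whether SD-005 already reports these events is unknown, and so is whether SD-005 supplies were affected by the manufacturing problem.

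The contradiction between SAP 6.5.2 and 8.7.2 rests on no assumption and needs correcting in any case. Both parts are worth acting on because the correction is cheap and even one related serious event would matter. Neither shows that the main TEAE tables are wrongly anchored.

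**What to change.** 1. Keep the main TEAE and TESAE tables anchored on the first SD-006 dose for both groups. In the collection sentence of SAP 6.5.2, drop the qualifier 'treatment-emergent' so that it speaks of AEs collected from consent, and let 8.7.2 alone define treatment-emergence.
2. Add one supplementary table and listing, for the SD-101-6.0 → SD-101-6.0 group only, of events that start or worsen between the last SD-005 study day and the first SD-006 application. Show days since the last SD-005 application. Show serious events separately where seriousness is recorded in medical history or SD-005 data. Mark events already reported in SD-005 so that an integrated summary does not count them twice.
3. State in SAP 6.5.2 that these events are included in the planned medical review for possible product contamination.

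The cost is two SAP wording changes and a little more programming, using events that protocol 13.3 already has recorded at Visit 1. The continuing group's reported event count may rise slightly. Seriousness or causality may be missing for events held only as medical history, and the table should say so.
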